2.3. Exploratory Objective

1. To determine whether it is possible that use of GC will result in an overall reduced net cost to the healthcare system by avoiding treatment in many patients.

3. Study Design

This is a 4-5 year (up to 2 years enrollment , 3-year follow-up) prospective, cluster-crossover, unblinded, study of 550 subjects from at least fourteen centers of the Michigan Urological Surgery Improvement Collaborative (MUSIC), a physician-led quality improvement consortium comprised of the vast majority of urology practices within the state of Michigan.

According to the cluster-crossover design, each participating MUSIC clinical center within MUSIC will be randomized to either a Genomic Classifier care-based (GC) or Usual-Care-based (UC) strategy for a period of 3 months, during which all enrolled subjects within the center will be provided the assigned strategy. Random assignments will be generated centrally by a study statistician and provided to centers immediately before commencing enrollment in each 3-month period. The randomization will be based on a random block size of either 2 or 4. This will ensure that each center will have two periods of GC and two periods of UC during the enrollment period, maintaining study-wide balance and blinding of assignments in subsequent periods.

If enrolled during the GC period, both subjects and their treating physician will be provided GC (from GenomeDx) and CAPRA-S (from MUSIC-Central) to inform their treatment plan. In the UC periods, only the CAPRA-S results, provided by MUSIC-Central, will be available. Blinding of subjects and treating physicians will not be possible given the nature of the information.

Subjects enrolled to the GC arm will receive MUSIC-led education about the GC test. The pros and cons of the GC test need to be described by an unbiased clinician scientist including the past history of the test (published studies).

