5.3. Exploratory Endpoint

Cost comparison/difference between GC and UC care at 3 years after surgery

6. Assay Specimen Requirements and Logistics

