7.3. Statistical Methods Supporting the Secondary Objectives

All tests will be two sided at a 0.05 significance level. Individuals who are lost to follow-up will be considered censored in time to event analyses. Treatment plans available at the time of drop-out will be considered the final treatment plans.

Secondary Objective 1: To determine whether the net benefit to subjects in the GC arm is superior to the UC arm. This will be determined by directly calculating the net benefit (Vickers and Elkin 2006) across a range of treatment thresholds, Decision Curve Analysis (DCA). DCA is a method for assessing prognostic models that incorporates clinical consequences and the potential probability thresholds at which the likelihood of a given outcome (eg: progression to metastatic disease) may influence the treatment decision of a patient and their physician. For example, one individual may choose treatment if there is a 5% chance of a given outcome while another individual may not be influenced unless the likelihood of that outcome is as high as 10 or 15%. Thus, this methodology allows for how different patients may differentially weigh false negative or false positive results. The calculated net benefit is plotted against threshold

probabilities, and different prediction tools (eg. CAPRA-S and GC) can be compared across these probabilities. If GC is not superior to UC across all thresholds, the region of superiority will be evaluated to determine if it contains a clinically meaningful ratio of harm due to unnecessary treatment versus missed treatment.

Secondary Objective 2: To determine whether use of the GC test result results in decreased likelihood of treatment for CAPRA-S high and increased likelihood of treatment for CAPRA-S low, a modeling approach similar to that of supporting the Primary Objective will be used, but with a GC-by-CAPRA-S interaction term as follows:

$$\text{logit}\left(\frac{\pi_{ijk}}{1-\pi_{ijk}}\right) = \beta_0 + \beta_1 G_i + \beta_2 (G_i * GC_i) + \beta_3 CAPRA-S_i + \beta_4 (G_i * CAPRA_i * GC_i) + \gamma_j + \phi_k$$

where parameters are defined as previously. The test of $H_0: \beta_4 = 0$ will be performed using a Type III test (SAS PROC GLIMMIX). The direction of the interaction will be evaluated graphically with the probability of treatment based on the model and for empirical probabilities using pre-defined GC and CAPRA-S cutoffs.

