Secondary Objective 3: Time-to salvage therapy initiation will be modeled using a Cox formulation of a Frailty regression model with a similar formulation (ie: main and random effects) to that used for the primary analysis. Kaplan-Meier curves for GC and UC arms will be plotted, as well as for combinations of high- and low-risk GC and CAPRA-S groups.

Secondary Objective 4: Time-to BCR and metastatic progression will be evaluated similarly to the model described for Secondary Objective 3.

Secondary Objective 5: Summary statistics for all QOL instruments and corresponding confidence intervals will be calculated and compared for the GC and UC subjects and shown graphically over time. Validated instruments are used to measure erectile function, urinary function, sexual interest, and sexual satisfaction. Scores for each domain will be scaled with a minimum to maximum range of 0-100. Comparisons between GC and UC subjects will be made at each timepoint (3, 6, 12 and 24 months after surgery) and on each domain and overall score (VAS 0-10), using an ANCOVA analysis including adjustment for time since surgery. Should the assumptions for ANCOVA not be met (strongly skewed data or substantial ceiling or floor effect) a semiparametric ANCOVA model will be used (as in Buja 1989) to adjust for time-from surgery. If the distribution of time-from surgery is similar in the two groups, a Mann-Whitney test for differences will be used to corroborate the ANCOVA model. For this secondary objective, there will be no adjustment for multiple comparisons across domains or time points.

Exploratory Objective: Using a variety of budget models the cost of care for patients in the GC vs. UC arms will be compared out to 3 years from surgery. This will include estimated costs for adjuvant therapy. Differences in total cost, and differential cost per patient (UC vs GC) will be calculated and compared using either standard t-tests if data is normally distributed or appropriate non-parametric test if data is right skewed.

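### For skewed costs the plan permits a rank test, which does not test the difference in total or mean cost and could point the other way

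*Combined protocol and SAP*

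**What the plan says.** Section 2.3 asks whether "use of GC will result in an overall reduced net cost to the healthcare system by avoiding treatment in many patients". Section 5.3 gives the endpoint as "Cost comparison/difference between GC and UC care at 3 years after surgery".

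Under the Exploratory Objective, Section 7.3 says "Differences in total cost, and differential cost per patient (UC vs GC) will be calculated and compared", and makes the test depend on the shape of the data: "using either standard t-tests if data is normally distributed or appropriate non-parametric test if data is right skewed". It does not name the non-parametric test or say how skewness will be judged. On components it says only "This will include estimated costs for adjuvant therapy"; the cost of the GC test is neither included nor excluded by name. Section 7.3 also sets the general rule that "All tests will be two sided at a 0.05 significance level".

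Section 3 describes an "unblinded, study of 550 subjects from at least fourteen centers", with centres randomised by 3-month period. The primary model in Section 7.1 has centre and period effects, and the time-to-event models in Section 7.3 follow its form. The cost comparison has neither effect.

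**The concern.** A question about net cost to the healthcare system is a question about totals, and so about arithmetic means: total cost is the mean multiplied by the number of patients. A test chosen because the data are skewed should still test that quantity. A rank test asks instead whether a randomly chosen GC patient tends to cost more than a randomly chosen UC patient.

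The two questions can have opposite answers here. If the assay is costed, every GC patient is shifted up by a small amount, while any saving sits in the few patients who avoid an expensive treatment. Ranks register the small shift in everyone and barely register the large saving in a few. At stake is a significant result for GC being dearer, printed beside a lower GC mean cost.

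**Working it through.** The plan states no sample size, power or cost figure for this comparison, so there is nothing of its own to reproduce.

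**Inputs from the documents.** 550 subjects (Section 3), taken as 275 per arm because allocation is about 1:1; two-sided 0.05 (Section 7.3); adjuvant rate about 8% in CAPRA-S high-risk MUSIC patients (Section 7.5).

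**Assumptions, in arbitrary cost units.** Assay cost c = 1 for each GC patient; treatment cost T = 20 or 30; UC/GC adjuvant rates 12%/6% or 8%/4%; other 3-year costs lognormal with the mean and SD shown. Clustering is ignored.

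**Step 1: true mean difference.** GC minus UC = c − T × (p_UC − p_GC).

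- T = 20, 12% vs 6%: 1 − 20 × 0.06 = −0.2.
- T = 30, 8% vs 4%: 1 − 30 × 0.04 = −0.2.

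GC is cheaper on average in both settings.

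**Step 2: how often a Mann-Whitney test is significant for GC dearer.**

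| Other costs: mean, SD | T = 20, 12% vs 6% | T = 30, 8% vs 4% |
|---|---|---|
| 2, 1 | 100% | 100% |
| 5, 5 | 70% | 88% |
| 10, 5 | 21% | 41% |
| 10, 10 | 15% | 24% |
| 20, 10 | 4% | 8% |

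Repeat runs agree to within a point or two. In the last row the figure approaches the 2.5% expected in one direction by chance. In the first row, a Welch t-test called GC dearer in 1.3% and 0.8% of trials, and the observed GC mean was lower in 61–64% of trials, so the p-value and the reported means would conflict in most of them.

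**Step 3: no assay cost (c = 0).** The rank test called GC dearer in under 1% of trials. It detected the true saving in 10–24%, against 20–67% for Welch, and had less power in every setting.

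**Step 4: the mechanism by hand.** Take the extreme case of no other costs, T = 30 and c = 1, with 22/275 UC and 8/275 GC patients treated.

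- UC total = 22 × 30 = 660; mean 660/275 = 2.40.
- GC total = 275 × 1 + 8 × 30 = 515; mean 515/275 = 1.87.
- Mean difference = −0.53, so GC is cheaper.
- P(GC patient costs more than UC patient) = (267/275) × (253/275) + 8/275 = 0.92, with a Mann-Whitney p of about 5e-83 in the direction of GC dearer.
- Tests of the mean on the same data: permutation p = 0.35, Welch p = 0.36, bootstrap 95% CI −1.62 to 0.56.

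A permutation or bootstrap analysis of the mean is also non-parametric, and it does not reverse.

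**Step 5: clustering.** Section 7.5.1 assumes a site ICC of 23% for adjuvant treatment, a main driver of cost, and a 3% period correlation. Neither cost test uses centre or period. The documents give no ICC for cost, so the size of this effect is not estimated here.

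**The case against.** A reader might infer that the plan prescribes a Mann-Whitney test for cost. It does not. It asks for an appropriate non-parametric test, which a permutation or bootstrap test of means would satisfy. Where Section 7.3 wants Mann-Whitney it names it, for quality of life. This objection stands: the rank test is permitted, and is the usual reading after a t-test for normal data, but it is not required.

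A reader might also infer that the analysis would give the wrong answer on net cost. It would not lose the answer. The total and per-patient differences are to be calculated whichever test is used, so only the p-value would mislead.

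Nor do the documents support treating reversal as near-certain. They give no cost figures and do not say that the assay is costed. The 100% result needs an assay cost as large as one SD of all other 3-year costs. Care over 3 years could include salvage treatment and management of recurrence, which would widen that SD and shrink the effect, as Step 2 shows.

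Finally, the 8% rate is for CAPRA-S high-risk patients, not all subjects. It supports expecting skew but is not the trial-wide rate.

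What survives is that the permitted test does not match the stated quantity, in the case most likely to arise. Exploratory status lowers the stakes but does not remove the mismatch.

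**Conclusion.** The point holds as a minor one. The plan's target is a difference in total and per-patient cost, yet for right-skewed data it leaves the test open to one that does not address that target. A wrong-direction significant result is possible only if the assay cost is counted and is not small against the spread of other costs. Under the assumed costs its frequency ran from about 5% to 100%. If the assay is not counted, the consequence is lost power, not reversal. All these frequencies rest on assumed costs and treatment rates and on independent patients. The lack of any allowance for centre and period applies to both branches, whichever test is chosen.

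**What to change.** In the Exploratory Objective paragraph of Section 7.3:

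- Delete the choice of test by normality or skewness.
- Name the estimand: the difference in arithmetic mean cost per patient, GC minus UC, at 3 years after surgery, whatever the skew.
- Give a bootstrap confidence interval that resamples centres. Alternatively, fit a gamma model with log link and centre and centre-by-period effects, back-transformed to mean cost.
- State that the assay cost is included in the net cost of the GC arm.

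The cost is a few lines of SAP wording and slightly more analysis work. Intervals may be wider than from a test that ignores centres, and with about fourteen centres a resampling interval will be somewhat rough. No change to data collection, sample size or the primary analysis is needed.

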7.4. Power and Sample Size

There are no existing computer packages that can determine the power or sample size for a parameter in a mixed-effect logistic model from a cluster-crossover trial. As a result, power and sample size estimates were determined through large-scale simulation utilizing the model and analysis method described in Section 7.1.

7.5. Simulation settings

In order to determine plausible values of the parameters of the model described in Section 7.1, several clinical utility studies of the GC were pooled and utilized in a re-sampling routine to determine likely values of parameters for the current study. Although none of the previous clinical utility studies were randomized comparative trials, the DECIDE (Badani 2013), ASSESS-D (Badani 2014), and PRO-ACT Michalopolous (2014) studies did involve real high-risk patient cases (only those that were pT3 or SM+ are included here) from community and tertiary care facilities and can be expected to provide similar clinical and genomic characteristics to those eligible for this trial. In all studies, treatment recommendations were provided by physicians initially without GC risk scores then (in a blinded fashion) with knowledge of both clinical and GC risk.

There are a total of 530 recommendations with and without GC available from these clinical utility studies. To approximate a parallel-group (GC and UC) randomized trial, for each run of the re-sampling routine, the data was randomly halved, taking half of the recommendations made with knowledge of the GC ($n = 265$) and the other half with recommendations made without knowledge of the GC ($n = 265$). Ten-thousand such data sets were generated and to each, a generalized linear model of the probability of treatment was fit, similar to that described in Section 7.1 but involving only the fixed effects. Across these 10,000 samples, the mean ORs of GC score, CAPRA-S score, and arm (GC vs UC) are, respectively, 1.47, 1.15, and 0.24. The overall rate of adjuvant treatment of CAPRA-S high-risk patients in MUSIC clinics is ~8%.

7.5.1 Power and Sample Size Simulation

Generating CAPRA-S and GC Scores

Simulation was used to determine the sample size necessary to have adequate power to reject the null hypothesis, $H_0: \beta_2 = 0$, based on the model in Section 7.1. CAPRA-S and GC risk scores for the simulated datasets were based on the distributions observed in the PRO-ACT clinical utility study (Michalopolous 2014). The distribution of CAPRA-S risk in PRO-ACT clinical is similar to that of MUSIC (62.7% vs 55.8% low risk and 44.2% vs 37.3% high risk). The distribution of GC risk scores among MUSIC patients is unknown, but due to the similarity in CAPRA-S scores, it is assumed that it will also be somewhat similar to PRO-ACT.

To ensure a) the GC score distribution is comparable to PRO-ACT, b) the CAPRA-S risk distribution is as similar as possible to MUSIC, c) the true variability of the continuous GC score, and d) the underlying correlation between GC and CAPRA-S risk is maintained, the following procedure was used to generate GC and CAPRA-S scores for each simulated individual:

1. A random percentile is generated (0-100%) and rounded to the nearest 5%.
2. PRO-ACT scores with GC score (and corresponding CAPRA-S score) within that percentile range (eg: 20-25th percentile) are then selected.
3. A GC score is then generated as a uniform a random number between the maximum and minimum of the selected PRO-ACT GC scores.
4. An initial CAPRA-S score is then randomly sampled from the selected CAPRA-S scores. The initial CAPRA-S score is then incremented by 1-point (to a maximum of 12) with 75% probability to up-adjust the slightly lower risk in PRO-ACT.

Generating Enrollments

Based on data available from MUSIC-central, the peak performing clinical centers exceeded 10 radical prostatectomy cases per month, with case-loads below 5 per month for the 4th and 5^h centers. Enrollments per site*month were generated using a Poisson process using the following conservative means: Site 1: 10, Site 2: 10, Site 3: 5, Site 4: 5, Site 6-8: 4, Site 9 and higher: 2.

Sites were randomized to enroll subjects to the GC or UC arm for each period using a fixed-block size enrollment (2, 3, or 4 depending on the randomization ratio of the simulation). Period length varied from month to year.

Intra-Class Correlations

In other clinical utility studies on GC (eg: Badani 2014) physicians reviewed several cases. With physicians as clusters, the ICC in this study is approximately 38% using methods of Wu (2012). In somewhat different scenarios, and with alternative methods of calculation Adams (2004) identified the IQR of ICCs as 3.5-28.4% in cluster-randomized trials. Assuming that the ICC for an entire clinical center will be less than for a single physician, and given the findings of Adams, an ICC of 23% was selected for the simulation – given the other parameter settings of the model, specified above, this is equivalent to setting $\rho^2 = 1$. A small intra-period (across sites) is also incorporated (ICC = 3%) to include the possibility of a temporal correlation across sites - potentially related to changes in educational materials or seasonal trends.

7.5.2 Simulation Results

Partial simulation results are listed in Table 1. Five-thousand simulated datasets were generated and analyzed at each setting – simulation error is ~ 0.5%. Various combinations of the site-ICC, number of sites, duration of randomization periods, and sample size were attempted. A study of 350 subjects at 14 clusters (centers) enrolled over 3-month periods equally randomized to GC or UC, will have 83% power to detect a significant CAPRA-S-adjusted effect of GC score on the likelihood of adjuvant therapy at the 0.05 level. Such a study will require 8-12 months (ie: 3-4 periods) for recruitment.

Minor perturbations in the ICC (15-35%), number of sites (5-10), and the randomization period duration (1-4 months) did not effect the power by more than 1%, with a sample size of 350. However, including 4 or fewer sites will result in a power < 80% and while inclusion of 8 or

more sites will maintain the desired power (> 80%), inclusion of these lower-recruiting sites will not appreciably decrease the enrollment period.

Additional components influencing the required sample size are the total event rate, average and variance of site-period recruitment, and actual approximation of the randomization ratio (will not be exactly 1:1). These, as well as the site-ICC, will be evaluated as described in Section 7.2, Sample Size Re-Estimation.

Table 1: Power comparisons for various sample sizes.

Site-ICC	Number of Sites	Period Duration (months)	Approx. Duration of Enrollment (months)	Sample Size	Power
23%	8	3	6	200	47%
23%	8	3	6	250	60%
23%	8	3	7	300	77%
23%	8	3	8	350	83%
23%	8	3	9	400	88%
23%	8	3	12	500	93%

8. Confidentiality and Ethical Issues

The Principal Investigators are responsible for conducting this Study Protocol. The study will be reviewed and approved by an IRB/EC and appropriate Scientific Review Committees prior to initiation.

All participating physicians must sign a confidentiality and non-disclosure agreement.

9. Scientific Presentation and Publication Policy

Presentation and publication of the results will be based upon appropriate analysis and review of the complete data, and the usual rules for determining authorship will guide scientific presentation and publication of the results of this study. Written approval from GenomeDx Biosciences is required prior to disclosing any confidential information relative to this study.

10. Data and Safety Monitoring

This study will be monitored in accordance with the NCI approved University of Michigan Comprehensive Cancer Center Data and Safety Monitoring Plan.

The study team will meet every six months or more frequently depending on the activity of the protocol. The discussion will include matters related to the safety of study participants (SAE/UaP reporting), validity and integrity of the data, enrollment rate relative to expectations, characteristics of participants, retention of participants, adherence to the protocol (potential or real protocol deviations) and data completeness. At these regular meetings, the protocol specific Data and Safety Monitoring Report form will be completed and signed by the Principal Investigator or by one of the co-investigators.

Data and Safety Monitoring Reports will be submitted to the University of Michigan Comprehensive Cancer Center Data and Safety Monitoring Committee (DSMC) every six months for independent review.

11. References

Adams, Geoffrey, Martin C. Gulliford, Obioha C. Ukoumunne, Sandra Eldridge, Susan Chinn, and Michael J. Campbell. "Patterns of intra-cluster correlation from primary care research to inform study design and analysis." *Journal of clinical epidemiology* 57, no. 8 (2004): 785-794.

Badani, Ketan, Darby JS Thompson, Christine Buerki, Elai Davicioni, Jill Garrison, Mercedeh Ghadessi, Anirban P. Mitra, Penelope J. Wood, and John Hornberger. "Impact of a genomic

classifier of metastatic risk on postoperative treatment recommendations for prostate cancer patients: a report from the DECIDE study group." *Oncotarget* 2013; 4(4): 600-9.

Badani, Ketan K., Darby J. Thompson, Gordon Brown, Daniel Holmes, Naveen Kella, David Albala, Amar Singh, Christine Buerki, Elai Davicioni, and John Hornberger. "Effect of a genomic classifier test on clinical practice decisions for patients with high-risk prostate cancer after surgery." *British Journal of Urology Intl* 2014; 115(3): 419-429.

Campbell, Michael J., and Stephen J. Walters. *How to Design, Analyse and Report Cluster Randomised Trials in Medicine and Health Related Research*. John Wiley & Sons, 2014.

